## Introduction

Retrospective studies have defined fitting characteristics and indications for the use of rigid gas permeable scleral lenses over the past three decades. These lenses have traditionally been used for visual rehabilitation in cases of corneal surface irregularity and in the management of severe ocular surface disease. Long-term use of topical medication in the management of glaucoma can cause chronic epithelial irregularity or even frank epithelial defects. Thus, patients who must use these medications to lower intraocular pressure may experience discomfort due to these symptoms. Scleral lenses can protect the ocular surface, and may allow the epithelium to heal. Although patients with glaucoma or ocular hypertension have undoubtedly been fit with scleral lenses, the effect of scleral lens wear on intraocular pressure in patients with glaucoma have not been specifically reported.

The defining fitting characteristic of scleral lenses is that they land upon the conjunctival tissue that overlies the sclera, and completely vault the cornea and limbus. The haptic, or landing zone, of a scleral lens may exert posteriorly-directed pressure on the sclera overlying the trabecular meshwork and vascular structures associated with aqueous humor drainage. The amount and location of this posteriorly-directed pressure depends upon lens diameter. Smaller-diameter lenses feature relatively narrow landing zones which impact tissue relatively close to the limbus, less landing zone contact area could lead to greater pressure per unit area. Indeed, smaller lenses appear to settle more than larger lenses during wear, which could potentially lead to more distortion of structures within the angle. Large-diameter lenses have relatively wide landing zones that tend to be farther from the limbus. This characteristic may make distortion of angle structures less likely with large-diameter lenses. However, the wide haptics that characterize large-diameter lenses may inhibit aqueous outflow through the episcleral venous system. Some have speculated that scleral lens wear could potentially affect intraocular pressure.

## Background and significance:

We previously studied the use of small diameter lenses and found no change in IOP with two hours of continuous lens wear. In this study, IOP was measured by pneumatonometry peripherally (on the sclera, 2mm temporal to the limbus) in the study eye with a scleral lens on, and compared to the peripheral IOP of the contralateral eye, with no scleral lens wear, at the same times. There were no differences in IOP between peripheral IOP measurements between the eye wearing the lens or the control eye without the lens. Central and peripheral IOP in these eyes were not different before or after 2 hours of lens wear. Peripheral IOP, measured higher in both eye, similar to other studies. However, the study population was relatively young, and had no history of eye disease. The development of

scleral changes in some elderly individuals suggests that scleral rigidity may change over time. This could change the dynamics of scleral influence on aqueous humor outflow and be of concern particularly in individuals with ocular hypertension.

Ocular surface rigidity can be measured using the ocular response analyzer and ultrasound surface wave elastograph. Ocular surface rigidity could affect the settling of scleral lenses, and could thus influence the amount of settling, and amount of potential pressure the scleral lens may place on the aqueous drainage structures of the eye. Settling of scleral lenses can be measured through Scheimpflug images obtained by Pentacam. The Pentacam program has a caliper tool that may be used to measure the distance between the back surface of the scleral lens and the front surface of the eye. This process has been used to measure settling of scleral lenses in previous studies.

A recent study measuring IOP during scleral lens wear, using a diaton to measure IOP found an increase in IOP with short-term scleral lens wear.

One other study has explored ramifications of scleral lens wear in patients with glaucoma, but concentrated on preferred shunt placement in scleral lens patients who required glaucoma filtering surgery.

We hypothesize that scleral lens wear will not exert enough pressure onto the scleral and ocular structures of the eye to raise IOP in patients with ocular hypertension over 2 hours of scleral lens wear.

### **Specific Aims:**

#### **Specific Aim 1:**

To determine if 4 hours of small diameter scleral lens wear will not create enough pressure to underlying trabecular meshwork and/or episcleral veins structures to create a statistically significant increase in intraocular pressure in patients with ocular hypertension.

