**Procedure:**

1. During initial evaluation, patient will be fit with a 15.0 mm diagnostic scleral lens which provides 300-400 microns of clearance immediately after lens application. (We expect lens to settle, which would leave 200-300 microns of clearance). The lens will be fit to one eye, randomly selected. No modifications will be made to lenses of the fitting set, so vision will not be corrected with the lens. The peripheral fit of the lens will be recorded.
2. At study visit:
  - a. A series of three measurements of corneal hysteresis with (ORA)
  - b. A series of three measurements of corneal elasticity with ultrasound surface wave electrography prototype
  - c. IOP will be measured centrally and peripherally by pneumotonometry, in each eye before lens wear. The control eye will be measured centrally and temporally every half hour for 4 hours.
  - d. IOP will also be measured through the eyelid with a diatom on each eye. The non-lens wearing eye will serve as a control for the eye wearing the scleral lens.
  - e. Lens will be applied to the study eye.
  - f. IOP will be measured in the temporal quadrant just beyond the edge of the scleral lens by pneumotonometry immediately after lens application, and every 30 minutes for 4 hours of lens wear. Central and peripheral IOP will be measured in the study eye immediately after lens removal.
  - g. IOP will also be measured through the eye lid after lens application, every half hour for four hours after lens wear, and again after lens removal.
  - h. Pentacam images will be obtained prior to lens application, immediately after lens application and every half hour after lens application; immediately before lens removal, and after lens removal.

Participant reimbursement: Participants will receive \$100 for completing the study visit, along with reimbursement for parking expenses during study visits.

Risks:

There are no more risks to this study than there are for any general eye exam. Proparacaine drops will be used for the IOP measurements, these drops are often used in general eye exams. There is a small risk of allergic reaction to the drops, but it is rare. Likewise, the IOP measurements or scleral lens placement or removal could induce a corneal abrasion. IOP measurements are measured frequently with rare abrasions. Scleral lenses are often fit on fragile eyes, with rare complication.

Data analysis:

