All analysis will be completed using paired t-test IOP prior to lens wear will be compared to IOP during lens wear and following lens removal.

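### Aim 1 seeks a no-increase conclusion but makes the absence of a significant paired t-test its only criterion, with no limit that the result must exclude

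*Combined protocol and SAP*

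**What the plan says.** The hypothesis in Background and significance is one of no effect: "We hypothesize that scleral lens wear will not exert enough pressure onto the scleral and ocular structures of the eye to raise IOP". Specific Aim 1, the only aim, is to determine whether lens wear "will not create enough pressure to underlying trabecular meshwork and/or episcleral veins structures to create a statistically significant increase in intraocular pressure". (The hypothesis refers to 2 hours of wear and Aim 1 to 4 hours; nothing below depends on that difference.)

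The analysis plan is a single statement under Data analysis: "All analysis will be completed using paired t-test", with the contrast described as "IOP prior to lens wear will be compared to IOP during lens wear and following lens removal". The during-wear readings are taken "by pneumotonometry immediately after lens application, and every 30 minutes for 4 hours of lens wear".

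The Power Statement gives 21 subjects for detecting a 2 mmHg elevation, with a mean daytime IOP of 13.8 ± 2.8, an α error of 5% and a β error of 10%. It does not say whether the test is one- or two-sided. It does not call 2 mmHg an acceptable rise or a margin. The document contains no confidence-interval rule and no equivalence or non-inferiority test.

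**The concern.** The investigators expect a null result, and Aim 1 builds statistical significance into its wording. Read literally, the aim is met whenever the paired t-test shows no significant increase, however wide the interval around the estimate. A non-significant test does not show that a rise is small. Noisier data or fewer completed subjects would make the hoped-for result easier to reach: at an SD of change of 2.8 mmHg and a true 2 mmHg rise, non-significance occurs 12% of the time with 21 subjects and 48% of the time with 10.

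At stake is the conclusion of the only aim. The trial could report that lens wear does not raise IOP in ocular hypertension from data that remain compatible with the 2 mmHg rise it was sized to detect.

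**Working it through.** **Inputs.** From the Power Statement: n = 21, difference 2 mmHg, α = 5%, β = 10%, and 2.8 mmHg, taken as an SD. Assumptions: one before-versus-during contrast, a two-sided test, and 2.8 as the SD of the within-eye change. The last is an assumption because the plan attaches 2.8 to a mean IOP level. If 2.8 is the SD of level, an SD of change of s implies a within-eye correlation of 1 − s²/(2 × 2.8²): 0.74 for s = 2.0, 0.50 for 2.8 and 0.22 for 3.5. These three values are used as the range.

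**1. Reproduce the plan's figure.** Normal approximation for a paired difference, two-sided:

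n = ((1.960 + 1.282) × 2.8 / 2)² = 20.6, rounded up to 21.

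The stated sample size therefore reproduces as a calculation for detecting a difference. With the exact t-test (noncentral t), power at n = 21 is 87.5%, so a true 2 mmHg rise is missed 12.5% of the time. Exact 90% power needs n = 23.

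**2. Precision.** SE = 2.8/√21 = 0.611 mmHg and t(0.975, 20 df) = 2.086, so the 95% CI half-width is 2.086 × 0.611 = 1.27 mmHg. It is 0.91 at SD 2.0 and 1.59 at SD 3.5.

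**3. When a null does not exclude 2 mmHg.** An observed mean rise is non-significant if it is below the half-width. Its upper limit is at least 2 mmHg if it is at or above 2 minus the half-width. With an observed SD of 2.8, both hold from 2 − 1.27 = 0.73 to 1.27 mmHg. For example, a mean rise of 1.2 mmHg gives t = 1.2/0.611 = 1.96, p = 0.064 and a 95% CI of −0.07 to 2.47. Aim 1 would be met, yet 2 mmHg is not excluded. The two conditions cannot both hold if the half-width is below 1 mmHg, that is, if the observed SD is below √21/2.086 = 2.20 mmHg.

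**4. How often.** Simulated probability that the test is non-significant and the upper 95% limit is 2 mmHg or more, n = 21:

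| True rise (mmHg) | SD 2.0 | SD 2.8 | SD 3.5 |
|---|---|---|---|
| 0 | 0.3% | 10.2% | 27.3% |
| 0.5 | 2.0% | 24.2% | 44.6% |
| 1.0 | 3.8% | 32.2% | 52.5% |
| 1.5 | 2.0% | 24.2% | 44.6% |
| 2.0 | 0.3% | 10.2% | 27.2% |

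**5. What an interval rule would give.** Conclude no relevant rise only if the upper limit of the two-sided 95% CI is below 2 mmHg. Power is the probability that a noncentral t (20 df, noncentrality (2 − true rise)/0.611) exceeds 2.086. At SD 2.8 this is 87.5% at a true rise of 0, 65% at 0.5 and 34% at 1.0 mmHg. The first figure equals the existing t-test's power in step 1, because both use noncentrality 2/0.611 = 3.27. If the true rise is exactly 2 mmHg, the rule would wrongly conclude no relevant rise 2.5% of the time by construction, against the 12.5% of such trials that would meet Aim 1 as written.

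**The case against.** **The trial is powered against 2 mmHg.** This largely stands. If the SD of change is 2.8 mmHg, a true 2 mmHg rise is missed 12.5% of the time against a planned 10%, and the gap comes from the normal approximation. But power is a planning property that rests on an assumed SD. Only the observed interval shows what the data exclude, and the plan does not require one.

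**The large percentages are not wrong conclusions.** This stands in full. A reader might infer from the table that the plan reaches a false answer up to a third of the time at SD 2.8. It does not. The 24% and 32% figures apply to true rises of 0.5 to 1.5 mmHg, where a statement that the rise is below 2 mmHg would be correct. They count nulls that cannot support that statement.

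**The size depends on an SD that the plan does not give.** This also stands: the range runs from 0.3% to 52%, and the problem disappears if the observed SD is below 2.20 mmHg. The missing rule is certain; how often it would matter is not.

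**The misuse is inferred.** Aim 1 is framed as a question, no section says that non-significance will be reported as no rise, and nothing forbids reporting an interval. That is fair, so it should not be said that the investigators intend that reading. But Aim 1's wording supplies a criterion, the hypothesis predicts the null, and no other criterion is offered.

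**The sample size must be wrong.** A reader might infer this too. The documents do not support it: 21 reproduces for the stated purpose, and the interval rule with a 2 mmHg margin has the same power when the true rise is 0.

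**Conclusion.** The point holds as a gap in the decision rule. The only aim seeks a no-increase conclusion, its only criterion is a non-significant paired t-test, and 2 mmHg enters only the sample size. A null that excludes 2 mmHg and one that does not would therefore count the same.

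At n = 21, with one contrast, a two-sided 5% test and an SD of change of 2.8 mmHg, between 10% and 32% of trials would end in a null that leaves 2 mmHg open, for true rises from 0 to 2.0 mmHg. Protection against missing a true 2 mmHg rise is close to what was planned. The finding does not show a high error rate or a faulty sample size. It should be settled before the data are seen, because a margin chosen afterwards would carry little weight.

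**What to change.** In Specific Aim 1 and Data analysis:

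- Prespecify one primary before-versus-during contrast from the readings already planned, and report its mean change with a two-sided 95% CI whatever the p-value.
- Conclude no relevant rise only if the upper limit is below a margin that the investigators prespecify and justify. The 2 mmHg design difference is a candidate, but the plan does not describe it as acceptable, so it needs a reason.
- If the test is non-significant but the upper limit reaches the margin, report the result as inconclusive.

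In the Power Statement, restate power for this rule. With a 2 mmHg margin, n = 21 and SD 2.8 it is 87.5%, 65% and 34% at true rises of 0, 0.5 and 1.0 mmHg.

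The cost is wording; no new measurements or enrolment are needed. The downside is lower stated power if lens wear causes a small true rise. The step from 90% to 87.5% at a true rise of 0 is not a cost of the rule, since the existing t-test already has that exact power against 2 mmHg.

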### **Study Design and Methods:**

#### **Inclusion:**

1. Diagnosis of ocular hypertension (IOP >22 in each eye during at least two visits over the previous 3 years)
2. May have had cataract extraction and IOL
3. Not on topical medication for glaucoma
4. No history of ALT/SLT
5. Any age, 18 years or older
6. History of contact lens wear (except scleral lenses), as long as they are willing to not wear their lenses the day of the study

**Exclusion:**

1. On topical medication for glaucoma
2. Eye disease
3. Inability to wear scleral lenses
4. Any intraocular surgery other than uncomplicated cataract extraction.
5. Known allergy to proparacaine eye drops.

**Variables collected:**

- Corneal thickness
- IOP prior to and during scleral lens wear; with Pneumotonometer and Diaton
- Pentacam images
- Ocular Response Analyzer (ORA)
- Ocular tissue elasticity by Ultrasound Surface Wave Elastography

**Procedure:**

1. During initial evaluation, patient will be fit with a 15.0 mm diagnostic scleral lens which provides 300-400 microns of clearance immediately after lens application. (We expect lens to settle, which would leave 200-300 microns of clearance). The lens will be fit to one eye, randomly selected. No modifications will be made to lenses of the fitting set, so vision will not be corrected with the lens. The peripheral fit of the lens will be recorded.
2. At study visit:
  - a. A series of three measurements of corneal hysteresis with (ORA)
  - b. A series of three measurements of corneal elasticity with ultrasound surface wave electrography prototype
  - c. IOP will be measured centrally and peripherally by pneumotonometry, in each eye before lens wear. The control eye will be measured centrally and temporally every half hour for 4 hours.
  - d. IOP will also be measured through the eyelid with a diatom on each eye. The non-lens wearing eye will serve as a control for the eye wearing the scleral lens.
  - e. Lens will be applied to the study eye.
  - f. IOP will be measured in the temporal quadrant just beyond the edge of the scleral lens by pneumotonometry immediately after lens application, and every 30 minutes for 4 hours of lens wear. Central and peripheral IOP will be measured in the study eye immediately after lens removal.
  - g. IOP will also be measured through the eye lid after lens application, every half hour for four hours after lens wear, and again after lens removal.
  - h. Pentacam images will be obtained prior to lens application, immediately after lens application and every half hour after lens application; immediately before lens removal, and after lens removal.

Participant reimbursement: Participants will receive \$100 for completing the study visit, along with reimbursement for parking expenses during study visits.

Risks:

There are no more risks to this study than there are for any general eye exam. Proparacaine drops will be used for the IOP measurements, these drops are often used in general eye exams. There is a small risk of allergic reaction to the drops, but it is rare. Likewise, the IOP measurements or scleral lens placement or removal could induce a corneal abrasion. IOP measurements are measured frequently with rare abrasions. Scleral lenses are often fit on fragile eyes, with rare complication.

Data analysis:

All analysis will be completed using paired t-test IOP prior to lens wear will be compared to IOP during lens wear and following lens removal.

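### The planned test is before-after only: it leaves out the lens-versus-control contrast that the design supports, and it names no primary device, site or summary

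*Combined protocol and SAP*

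**What the plan says.** The analysis plan is one short paragraph under Data analysis: "All analysis will be completed using paired t-test", and "IOP prior to lens wear will be compared to IOP during lens wear and following lens removal". It names no primary device, measurement site, time or summary of the repeated readings, and it has no rule for multiple tests.

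The measurement plan is much richer. Variables collected lists "IOP prior to and during scleral lens wear; with Pneumotonometer and Diaton". The Procedure for the study visit adds:

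- **Before the lens (2c):** "IOP will be measured centrally and peripherally by pneumotonometry, in each eye before lens wear".
- **Control eye (2c, 2d):** "The control eye will be measured centrally and temporally every half hour for 4 hours", and "The non-lens wearing eye will serve as a control for the eye wearing the scleral lens".
- **Study eye on lens (2f):** temporal readings "by pneumotonometry immediately after lens application, and every 30 minutes for 4 hours of lens wear".
- **Study eye after removal (2f):** "Central and peripheral IOP will be measured in the study eye immediately after lens removal".
- **Diaton (2g):** through-the-lid readings after application, half-hourly for four hours, and after removal.

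Specific Aim 1 and the Procedure refer to 4 hours of wear; the hypothesis that closes Background and significance refers to 2 hours. The Power Statement gives 21 subjects for a 2 mmHg elevation, with 5% alpha, 10% beta and a mean daytime IOP of 13.8 ± 2.8.

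**The concern.** A before-after test in the lens eye estimates the lens effect plus whatever else changes during the session. If IOP falls in both eyes over the 4 hours, a real lens-induced rise can be hidden. If it rises in both eyes, the lens can be blamed for it. The fellow eye is measured on the same schedule and could separate the two, but the stated comparison does not use it.

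The second gap is that nothing says which reading decides Aim 1. A mixed result is foreseeable from the protocol's own background: the team's earlier pneumatonometry study found no change over 2 hours, while a cited study using the Diaton found an increase. This trial uses both devices. If they disagree again, the plan has no answer, and the deciding device, site or time could be picked once the data are known.

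**Working it through.** **1. The plan's own figure.** Inputs from the Power Statement: difference 2, SD 2.8, alpha 5%, power 90%. For one paired contrast, normal approximation, two-sided:

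n = (1.960 + 1.282)² × 2.8² / 2² = 20.6, so 21.

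This reproduces the stated 21; one-sided 5% would give 16.8, so 17. The sample size therefore fits a single two-sided test with 2.8 used as the SD of the paired change, a label the Power Statement does not give it. With the exact t distribution, power at n = 21 is 87.5%, and 23 subjects give 90%.

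**2. Session change mixed with the lens effect.** One lens-eye test, n = 21, SD of change 2.8, two-sided 5% (t critical value 2.086 on 20 df). The noncentrality is (lens effect + session change) × √21 / 2.8. The documents give no session change, so 0.5 and 1 mmHg are assumptions.

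| Lens effect | Shared session change | Noncentrality | Chance of a significant rise |
|---|---|---|---|
| 2 | 0 | 3.27 | 87.5% |
| 2 | −0.5 | 2.45 | 64.7% |
| 2 | −1 | 1.64 | 34.4% |
| 0 | +0.5 | 0.82 | 11.9% |
| 0 | +1 | 1.64 | 34.4% |

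**3. How many study-eye tests the wording allows.**

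- Each reading tested separately: pneumotonometer 9 on-lens temporal (1 immediate + 8 half-hourly) + 1 peripheral and 1 central after removal = 11; Diaton 9 on-lens + 1 after removal = 10; total 21. This takes the half-hourly Diaton readings in 2g as made during wear, which is the evident sense.
- On-lens readings averaged per device: 2 averages + 3 post-removal values = 5.

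**4. Chance of at least one false rise.** Simulated with n = 21, no lens effect, each test two-sided 5%, and a false rise counted in the upper 2.5% tail. Blocks are the readings that share a pre-lens baseline (temporal or peripheral pneumotonometer 10, central pneumotonometer 1, Diaton 10). All correlations are assumed.

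| Correlation of changes within / between blocks | 21 tests | 5 tests |
|---|---|---|
| 0.7 / 0.3 | 21% | 9% |
| 0.8 / 0.5 | 16% | 8% |
| 0.9 / 0.6 | 12% | 7% |
| 0.9 throughout | 8% | 5% |
| Shared baselines, otherwise independent readings, independent blocks | 30% | 11% |

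A uniform correlation of 0.5 gives about 23% for 21 tests. One test gives 2.5%.

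**5. The lens-minus-control contrast.** Take 2.8 as the SD of change in one eye and c as the between-eye correlation of changes, which the documents do not give. The SD of the contrast is 2.8 × √(2(1 − c)).

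| c | SD | Power for 2 mmHg, n = 21 | 95% CI half-width (2.086 × SD / √21) |
|---|---|---|---|
| 0 | 3.96 | 60% | 1.8 |
| 0.3 | 3.31 | 75% | 1.5 |
| 0.5 | 2.80 | 88% | 1.3 |
| 0.7 | 2.17 | 98% | 1.0 |

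**The case against.** **The control eye is not forgotten.** A reader might infer that the protocol gives the fellow eye no role. That goes too far. Procedure 2c and 2d schedule its readings and call it a control, the earlier study compared the two eyes at the same times, and a paired t-test could be applied to pairs of eyes. The contrast looks intended. What stands is that the analysis paragraph defines only before-after comparisons, so followed as written it does not use the control.

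**Twenty-one is a maximum.** A reader might infer that 21 uncorrected tests will be run, with a 30% chance of a false rise. The plan does not say that each half-hour will be tested; averaging leaves 5 tests. The 30% treats two devices and two sites in the same eye and session as independent, so it serves only as an upper bound. No passage says that any single significant rise would count. Because the hypothesis is no rise, extra uncorrected tests also work against the team's own claim. Inflation is thus the lesser harm; the undefined answer is the larger one and depends on no correlation.

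**The drift figures illustrate a mechanism.** They do not measure this trial's risk, since the documents give no session change. This is fair and is why they are labelled as assumed.

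**The 2.8 may not be the right SD.** It stands beside a mean daytime IOP, and an average of eight readings would normally have a different SD from a single reading. This too is fair: the power figures show a range and do not predict this trial's power.

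**Conclusion.** The concern holds in two parts. First, the stated analysis is before-after only and omits the lens-versus-control contrast for which the readings are already scheduled, so session change is counted as lens effect. With an assumed SD of change of 2.8 and an assumed shared change of 1 mmHg, power for a 2 mmHg rise falls from 88% to 34%, or the false-rise rate reaches 34%. Second, no device, site or summary is primary, so 5 to 21 study-eye tests are open. The chance of any false rise is then roughly 5–21% under plausible assumed correlations (about 30% at most, with independent devices and sites), against 2.5% for one test. A disagreement between devices would leave Aim 1 without a defined answer.

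The documents do not show that drift will occur or that results will be picked selectively. Nor does this point show that more subjects are needed: power for the better contrast could be lower or higher than the planned 90%, depending on a between-eye correlation that is not given.

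**What to change.** Before analysis, replace the primary analysis with:

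- One paired t-test at two-sided 5% of the change from the pre-lens reading in the lens eye minus the same change in the control eye.
- Temporal pneumotonometry, averaged over the eight half-hourly readings scheduled in both eyes. The reading immediately after application is left out because 2c does not clearly schedule a matching one in the control eye. State that the pre-lens peripheral reading is the temporal baseline.
- The estimate with its 95% confidence interval, because a non-significant test does not show that there is no rise.
- Diaton, central, post-removal and single-time readings labelled secondary, with no confirmatory claim.

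Also reconcile the 2 hours in the hypothesis with the 4 hours in Specific Aim 1 and the Procedure.

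**Cost.** No new measurements are needed. The other readings lose confirmatory status. The Power Statement must be restated for this contrast, naming the SD and the between-eye correlation assumed; at N = 21 the stated 90% may not carry over (60% to 98% across the correlations shown). Restating that figure is what this point asks for; it does not require enrolling more subjects.
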